5.3.6.2 Adverse event collection and reporting

AE Collection

The Investigator shall maintain and keep detailed records of all Aes in their patient files. The following must be collected and documented on the appropriate CRF(s) by the Investigator:

- From signing the informed consent onwards through the Residual Effect Period (REP), until an individual subject's end of trial:
-all Aes (serious and non-serious) and all AESIs.
- After the individual subject's end of trial:
the Investigator does not need to actively monitor the patient for Aes but should only report relevant SAEs and relevant AESIs of which the Investigator may become aware of.

Proprietary confidential information © 2017 Boehringer Ingelheim International GmbH or one or more of its affiliated companies

[figure not shown]

Figure 5.3.6.2: 1 Illustration of Safety Reporting Requirements.

The REP is defined as _____ after the last trial medication application. All AEs which occurred through the treatment phase and throughout the REP will be considered as on treatment (see [Section 7.3.4](#)). Events which occurred after the REP and before next drug intake or trial termination date (whatever occurs first) will be considered as follow-up events.

AE reporting to sponsor and timelines

The Investigator must report SAEs, AESIs, and non-serious AEs which are relevant for the reported SAE or AESI, on the BI SAE form via fax immediately (within 24 hours) to the sponsor's unique entry point (country specific contact details will be provided in the ISF). The same timeline applies if follow-up information becomes available. In specific occasions the Investigator could inform the sponsor upfront via telephone. This does not replace the requirement to complete and fax the BI SAE form.

With receipt of any further information to these events, a follow-up SAE form has to be provided. For follow-up information the same rules and timeline apply as for initial information.

Information required

For each AE, the Investigator should provide the information requested on the appropriate CRF pages and the BI SAE form. The Investigator should determine the causal relationship to the trial medication.

The following should also be recorded as an (S)AE in the CRF and SAE form (if applicable):

- Worsening of the underlying disease or of other pre-existing conditions
- Changes in vital signs, ECG, physical examination and laboratory test results, if they are judged clinically relevant by the Investigator.

If such abnormalities already pre-exist prior trial inclusion they will be considered as baseline conditions.

Proprietary confidential information © 2017 Boehringer Ingelheim International GmbH or one or more of its affiliated companies

All (S)Aes, including those persisting after individual subject's end of trial must be followed up until they have resolved, have been sufficiently characterised, or no further information can be obtained.

Pregnancy

In rare cases, pregnancy might occur in a clinical trial. Once a patient has been enrolled in the clinical trial and has taken trial medication, the investigator must report any drug exposure during pregnancy in a trial participant immediately (within 24 hours) by means of Part A of the Pregnancy Monitoring Form to the sponsor's unique entry point.

Similarly, potential drug exposure during pregnancy must be reported if a partner of a male trial participant becomes pregnant. This requires a written consent of the pregnant partner.

The outcome of the pregnancy associated with the drug exposure during pregnancy must be followed up and reported to the sponsor's unique entry point on the Pregnancy Monitoring Form for Clinical Trials (Part B).

The ISF will contain the Pregnancy Monitoring Form for Clinical Trials (Part A and B). As pregnancy itself is not to be reported as an AE, in the absence of an accompanying SAE and/or AESI, only the Pregnancy Monitoring Form for Clinical Trials and not the SAE form is to be completed. If there is an SAE and/or AESI associated with the pregnancy an SAE form must be completed in addition

5.5 ASSESSMENT OF BIOMARKER(S)

Not applicable

5.6 OTHER ASSESSMENTS

There will be no additional assessments

5.7 APPROPRIATENESS OF MEASUREMENTS

All measurements performed in this trial are standard measurements to monitor safety aspects in an appropriate way. The primary and

Proprietary confidential information © 2017 Boehringer Ingelheim International GmbH or one or more of its affiliated companies

secondary endpoints are standard and accepted for evaluation of safety, tolerability, and are widely used in this kind of study.

The bolus MCh challenge method (see [Section 6.2](#)) has been chosen as this provides a consistent degree of muscarinic receptor excitation between treatment levels, allowing investigation of the effect of regular dosing with a therapeutic agent on both methacholine induced bronchoconstriction and subsequent recovery.

6. INVESTIGATIONAL PLAN

6.1 VISIT SCHEDULE

The trial consists of a screening period (Visit 1), pilot and main study periods (Visit 2 to 5) and end of study period (Visit 6). The pilot and main study each consist of four separate treatment periods. For administrative reasons, each of these four treatment periods within the pilot and main studies is referred to as a 'Visit' and each 'Visit' will consist of up to 3 days of procedures. The procedures conducted at each of the treatment period 'Visits' (Visit 2 to 5) are the same. A more detailed overview is provided in the [Flow Chart](#).

6.2 DETAILS OF TRIAL PROCEDURES AT SELECTED VISITS

Methacholine (MCh) challenge

The single methacholine concentration according to [Table 6.2.1](#) (column 4) will be administered at both Day -1 or Day -2 and Day 2 of each treatment period. This concentration needed to administer this dose considers the cumulative dose administered during the incremental challenge at the screening visit (see [Table 6.2.1](#)). Single FEV₁ measurements (FEV₁ only) are then made at 30 and 90 seconds, followed by duplicate FEV₁ and FVC measurements at 5, 10, 20, 30, 45 minutes, 1, 1.25, 1.5, 1.75, 2, 2.25, 2.5, 2.75 and 3 hours on Day -2 or Day -1, with additional timepoints at 3.5, 4.0, 4.5, 5.0, 6.0, 7.0 and 8.0 hours on Day 2.

Table 6.2.1: Incremental and bolus MCh challenge dosing schedule.

Dose Number	Methacholine Concentration during Incremental Challenge (mg/ml)	Cumulative Dose (mg) (rounded to 4 d.p. max)	Methacholine Concentration to be used to administer the Bolus Challenge (mg/ml) (only highest dose number administered at Visit 1)
1	0.03125	0.0014	0.03125
2	0.03125	0.0028	0.0625
3	0.0625	0.0056	0.125
4	0.125	0.0113	0.25
5	0.25	0.0225	0.5
6	0.5	0.045	1.0
7	1.0	0.09	2.0
8	2.0	0.18	4.0
9	4.0	0.36	8.0
10	8.0	0.72	16.0
11	16.0	1.44	32.0

Spirometry

Spirometry will be performed according to ATS/ERS guidelines for pulmonary function testing [[P05-12782](#)] in order to characterise the study population, to monitor individuals' safety in regard to asthma and as an exploratory assessment of drug effect. The subject must qualify by demonstrating a pre-bronchodilator clinic measured $FEV_1 \geq 70\%$ of predicted normal. FEV_1 normal predicted values will be calculated according to GLI [[R15-0845](#)] measured ≥ 8 hours after the last use of short acting bronchodilator at the screening visit (Visit 1) and treatment period 1 Day 1.

Equipment and techniques should conform to American Thoracic Society (ATS) criteria [[P05-12782](#)].

Spirometry will be conducted with the subject in a seated position. It is preferable that the same trained individual performs the PFTs for a given subject. Unless otherwise specified in methacholine challenges, the best of three efforts will be defined as the highest FEV_1 and the highest FVC each obtained on any of three blows meeting the ATS criteria (with a maximum of eight attempts). FEV_1 , FVC, will be measured as indicated in the [Flow Chart](#) and recorded in the eCRF. The best of the three pre-dose FEV_1 measurements will be defined as trough FEV_1 . The 24-hour clock time of the first manoeuvre for each PFT time point will be recorded.

Screening and run-in period(s)

After having been informed about the trial, all subjects will give their written informed consent in accordance with GCP and local legislation prior to enrolment in the study.

6.2.1 Treatment period(s)

Trial medication will be administered by each subject (under the direct supervision of the investigator or his designee). Details on treatments and procedures of administration are described are described in [Section 4.1.4](#).

All subjects will attend the trial site (see Flow Chart) after formal assessments and confirmation of their fitness by the investigator or designee.

For details on time points and procedures for collection of plasma samples for PK analysis (see Flow Chart).

The safety measures specified during the treatment period are specified in [Section 5.2](#) of the protocol and in the Flow Chart. For details on time points for all other trial procedures, refer to the Flow Chart. Aes and concomitant therapy will be assessed continuously from screening until the end of trial examination.

6.2.2 End of Trial Period

For AE assessment, laboratory tests, recording of ECG and vital signs, physical examination, see [Sections 5.3.1](#)

Subjects who discontinue treatment before the end of the planned treatment period should undergo the end of the trial visit.

All abnormal values (including laboratory parameters) that are judged clinically relevant by the investigator will be monitored using the appropriate tests until a return to a medically acceptable level is achieved. Adverse events persisting after trial completion must be monitored until they have been resolved or have been sufficiently characterised.

The end of the trial as a whole is defined by the 'last regular visit completed by last subject' or 'end date of the last open AE' or 'date of the last follow-up test' or 'date of an AE has been decided as sufficiently followed-up', whichever is the latest.

7. STATISTICAL METHODS AND DETERMINATION OF SAMPLE SIZE

7.1 STATISTICAL DESIGN – MODEL

The primary objective of the study is to investigate safety and tolerability of three consecutive administrations, 12 h apart, at three different dose-levels (100, 400 and 1200 µg) of BI 443651 administered via oral inhalation in male and female mild asthmatic subjects after a bolus MCh challenge.

For the main part, the primary endpoint absolute change in maximum reduction of FEV₁ and the secondary endpoint relative change in AUC_{0-tz} as described in [Section 5.1](#) will be analysed using a mixed effects model on the original and logarithmic-scale, respectively, taking the crossover design of the trial into account. The models will include treatment and period as fixed effects, subject as a random effect and period baseline as well as subject baseline as covariates. The subject baseline will be obtained by calculating the mean of period baselines for each subject. Active doses will be compared to placebo for both endpoints. For investigation of the secondary endpoint time to recovery to within 95% of post-diluent value a Cox proportional hazards model will be used to estimate the hazard ratio of BI 443651 vs. Placebo.

For the pilot part, the primary and secondary endpoints as described in [Section 5.1](#) will be analysed using descriptive statistics. No inferential statistics are planned for this part of the trial.

7.2 NULL AND ALTERNATIVE HYPOTHESES

Safety and tolerability of 3 different dose strengths of BI 443651 are to be determined on the basis of the investigated parameters in comparison to placebo. It is not planned to test any statistical hypotheses with regard to these variables in a confirmatory sense. Instead, they will be described in their entirety and evaluated by descriptive statistical methods.

Confidence intervals will be computed and will have to be interpreted in the perspective of the exploratory character of the study, i.e. confidence intervals are considered as interval estimates for effects.

7.3 PLANNED ANALYSES

All individual data will be listed.

Adherence to the protocol (such as inclusion/exclusion criteria, times of measurement, compliance with intake of trial medication, treatment dispensing errors, prohibited concomitant medication, completeness and consistency of data) will be checked. Important protocol violations (IPVs) will be identified no later than in the Blinded Report Planning Meeting and provided in the TSAP.

Proprietary confidential information © 2017 Boehringer Ingelheim International GmbH or one or more of its affiliated companies

The statistical analysis will be based on the following analysis sets based on the actual treatment the subject receives.

- Enrolled set (ES): This subject set includes subjects that signed informed consent and underwent screening procedures.
- Randomised set (RS): This subject set includes all randomised subjects, whether treated or not.
- Treated set (TS): The treated set includes all subjects who were randomised and treated with at least one dose of study drug. The treatment assignment will be determined based on the first treatment the subjects received.
- Methacholine set (MCS): This subject set includes all subjects in the treated set who provide at least one pair (baseline and end of treatment) of evaluable measures of spirometry parameters that were not excluded due to use of rescue medication within 3 hours after start of MCh challenge.

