- 1 This study (1363.7) will only start once healthy volunteers have been safely administered 100 and 400 µg b.i.d. of BI 443651 for 7days in a separate ongoing study (1363.2) i.e. no stopping criteria have been triggered in 1363.2.
- 2 Only mild, controlled, stable asthma subjects with well-maintained lung function will be included in the study i.e. subjects on prn SABA or low dose inhaled corticosteroid with an $FEV_1 \geq 70\%$ and no recent respiratory tract infection or exacerbation.
- 3 The study will be split into two parts ([see Section 3.1](#)) with an initial pilot (Part 1) to assess for gross adverse effects of BI 443651 on bronchoconstriction after MCh challenge. In Part 1, subjects will receive BI 443651 in a dose ordered fashion with either placebo **or** the lowest dose first followed by the higher doses and placebo (if not taken first). Individual subjects will not be dosed further if individual stopping criteria (including pulmonary function criteria) are triggered. Stopping criteria are described in detail in [Section 3.3.4](#).

The second part of the study (not necessarily dose ordered) will only proceed if no subjects triggered the first three discontinuation criteria following administration of BI 443651 during Part 1.

- 4 The subjects will be closely monitored throughout the treatment period with frequent evaluation of pulmonary function following MCh challenge. Subjects may only be discharged from clinic after medical assessment has been conducted. The subject's FEV_1 must have returned to $\geq 90\%$ of the first set of spirometry measurements performed that day before the subject can be discharged from the clinic. Rescue medication will be provided as required.
- 5 Safety laboratory testing will be performed during the study with a focus on electrolytes ([see Flow Chart](#)). The study will be stopped if, during Part 1 (pilot) at least 2 subjects in the current cohort or treatment period on active drug showed serum potassium levels $\geq 5.5\text{mmol/L}$ in non-haemolysed blood (confirmed by repeat). In Part 2 (main study), the study would be stopped if 4 subjects on active drug (independent of dose level) showed serum potassium levels $\geq 5.5\text{mmol/L}$ in non-haemolysed blood (confirmed by repeat).

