4.2.1.1 Rescue medication

Administration of rescue medication can occur at any point during the study. Open label salbutamol and /or atrovent MDI will be provided as rescue medication, at screening visit.

If rescue medication is administered during clinic visits (Visits 2– 5), the 24-hour clock time of rescue medication, total number of inhalations of rescue medication used, visit number, date and the name, route and dosage of any additional rescue medication will be recorded on the Rescue Medication eCRF page.

The use of rescue medication during Visits 2 -5 does not necessitate discontinuation of the visit. The subject should remain in the clinic in order to complete the remaining other procedures (see [4.2.2.2](#)).

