The secondary endpoint time to recovery of FEV₁ within 95% of post-diluent value (see [Section 5.1.2](#)) is defined as the time from maximum reduction to last time before recovery to within 95% of pre-MCh challenge during each challenge. The time obtained from the treatment challenge represents the endpoint, while the time obtained from the baseline challenge will be used for the baseline correction in the analysis.

This secondary endpoint will be investigated using descriptive statistics for both trial parts separately and combined, if applicable.

Kaplan-Meier (KM) curves will be plotted for the recovery of FEV₁ within 95% of post-diluent value by treatment irrespective of the period it is administered in, for both trial parts separately as well as combined, if applicable.

For part II of the trial, this endpoint will be analysed using a Cox proportional hazards model as given below based on the MCS. The model includes the treatment effect and an effect for subject baseline. Thereby, the subject baseline is calculated as median of all period baselines per subject. Breslow's method for handling ties will be used.

The hazard function for the ith subject is assumed to be

$$\lambda_i(t) = \lambda_0(t) \cdot \exp\{\beta_1 X_{1i} + \beta_2 X_{2i} + \beta_3 X_{3i}\},$$

where i = 1, ..., N,

$\lambda_0(t)$ is the unspecified, non-negative, baseline hazard function

- $\beta_{1,2,3}$ are the unknown regression coefficients
- X_{1i} represents the treatment group
- X_{2i} represents the subject baseline (median of period baselines)
- X_{3i} represents the period

Proprietary confidential information © 2017 Boehringer Ingelheim International GmbH or one or more of its affiliated companies

For treatment comparisons the hazard ratios of BI 443651 vs. Placebo and asymptotic 95% Wald confidence intervals will be estimated. A hazard ratio of greater than one means that BI 443651 is not inferior to placebo.

Further details will be provided in the TSAP.

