7.5 SECONDARY ENDPOINTS

The secondary endpoints will be analyzed based on the MCS.

Relative change from baseline in FEV₁ AUC_{0-tz} following bolus MCh challenge:

CTP: *The secondary endpoint relative change from baseline in FEV₁ AUC_{0-tz} (see Section 5.1.2 of the CTP) is defined as the ratio of FEV₁ AUC_{0-tz} obtained during the treatment challenge and during the baseline challenge. During each challenge, the area above the curve of the absolute change in FEV₁ from post-diluent value will be calculated from time 0*

to t_z using the trapezoidal rule (refer to 001-MCG-163). The time t_z refers to the last time point before recovery of FEV_1 to within 95% of post-diluent value.

Note that in case a subject's FEV_1 does not recover to within 95% of post-diluent value the time t_z refers to the last timepoint at which FEV_1 was measured for that subject in that period. Furthermore, if a subjects FEV_1 does not decrease below 95% of post-diluent value the AUC will not be defined and hence not be calculated.

Descriptive statistics and boxplots of the secondary endpoint by treatment (and by trial part) will be provided.

As main analysis, the following model will be applied to the main part of the trial (part II). The statistical model used for this secondary endpoints is comparable to the one specified for the primary endpoint, despite the fact that it is evaluated on the logarithmic scale.

Statistical model

CTP: [...] this secondary endpoint will be analysed using a mixed effects model on the logarithmic scale based on the MCS:

$$y_{imj} = \mu + \pi_m + \tau_j + \gamma b_{im} + \gamma' b'_i + s_i + e_{imj},$$

where $i = \text{subject } 1, \dots, N$, $m = \text{period } 1, \dots, 4$, $j = \text{treatment } 1, \dots, 4$

y_{imj}	Logarithm of CFB in FEV_1 AUC_{0-t_z} consideration for the i^{th} subject and the m^{th} period, receiving randomised treatment j
μ	overall intercept,
π_m	m^{th} period effect,
τ_j	j^{th} treatment effect,
b_{im}	Logarithm of baseline value for subject i in period m (period baseline),
γ	associated covariate effect of period baseline,
b'_i	Logarithm of the subject baseline value (mean of period baselines) for subject i ,
γ'	associated covariate effect of subject baseline,
s_i	the random effect of subject i ,
e_{imj}	the random error associated with subject i who received treatment j in period m .

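### No visible rule covers FEV1 read after rescue given 3 to 8 h after the Day 2 challenge; applied literally, the definitions would let such readings count as recovery

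*Protocol*

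**What the plan says.** - **Exclusion window.** Protocol 7.3 and SAP 6.3 admit to the Methacholine set subjects with at least one baseline and on-treatment pair of spirometry measures "that were not excluded due to use of rescue medication within 3 hours after start of MCh challenge". No other visible text links rescue to the challenge endpoints.
- **Follow-up.** The baseline challenge is read to 3 h. Day 2 has the same schedule "with additional timepoints at 3.5, 4.0, 4.5, 5.0, 6.0, 7.0 and 8.0 hours on Day 2" (Protocol 6.2), so seven readings fall after the exclusion window closes.
- **Rescue.** Protocol 4.2.1.1: "Administration of rescue medication can occur at any point during the study". A rescued subject stays on: "The subject should remain in the clinic in order to complete the remaining other procedures". The clock time of rescue at Visits 2 to 5 goes on the eCRF.
- **Discharge.** Protocol 2.3 requires FEV1 to be back to at least 90% of that day's first measurements "before the subject can be discharged from the clinic. Rescue medication will be provided as required".
- **Recovery.** Time to recovery "is defined as the time from maximum reduction to last time before recovery to within 95% of pre-MCh challenge during each challenge" (Protocol 7.3.2, repeated in SAP 7.5). The AUC runs to tz, the last reading before FEV1 is back within 95% of the post-diluent value. If FEV1 never gets there, SAP 7.5 says tz "refers to the last timepoint at which" FEV1 was taken in that period.
- **Censoring.** The PHREG code in SAP 9.2.1 uses `cnsr(1)`. No visible text says when the flag is set.

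**The concern.** The exclusion window matches the 3 h baseline schedule but not the 8 h Day 2 schedule. A subject still obstructed at 3 h can be rescued, stay in the clinic and continue with spirometry. Those later readings fall outside the stated exclusion, and the recovery definitions look only at the FEV1 level. A bronchodilator-driven return above 95% would then stop the recovery clock and fix tz. If FEV1 stayed below 95% despite rescue, the area to the last reading would still include treated values.

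The subjects exposed to this are the slow recoverers. Protocol 5.7 gives recovery after methacholine as one reason for choosing the bolus method, and the trial exists to look for cholinesterase-related harm. If active drug does slow recovery, more active than placebo periods would be affected, and the hazard ratio and AUC ratio would both move towards no effect.

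**Working it through.** **1. The plan's own figure.** The documents state nothing numerical for recovery time, rescue rate or hazard ratio. Their one precision figure (Protocol 7.7) is for the primary endpoint. With N = 32, SD 0.24 L and df = 3(32 − 1) − 3 = 90:

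t(0.95, 90) × 0.24 × √(2/32) = 0.0997 L; multiplied by √(χ²(0.95, 90)/90) it is 0.1118 L.

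This reproduces the stated 0.112 L. Nothing below changes it.

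**2. Timing.** The Flow Chart puts the Day 2 challenge at 25:00 and discharge at 33:00, so 33 − 25 = 8 h of observation. The rescue rule covers 3 h, leaving 5 h uncovered.

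**3. Hazard ratio.** All recovery and rescue inputs here are assumptions.

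- Recovery is exponential and read on the Day 2 schedule; 6,000 challenges per arm are treated as independent; Cox model with Breslow ties.
- Of those unrecovered at 3 h, 10% to 100% are assigned a rescue time uniform on 3 to 8 h. Rescue is given only if they are still unrecovered at that time.
- A rescued subject reads as recovered at the first scheduled reading at least 0.25 h later.

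True hazard ratio 0.5:

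| Placebo median | Unrecovered at 3 h, placebo / active | No rescue | Post-rescue readings counted | Censored at rescue |
|---|---|---|---|---|
| 0.75 h | 6.1% / 24.3% | 0.527 | 0.527–0.534 | 0.525–0.526 |
| 1.5 h | 24.8% / 49.4% | 0.522 | 0.528–0.585 | 0.520–0.526 |
| 3 h | 50.4% / 70.7% | 0.530 | 0.552–0.675 | 0.520–0.531 |

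The no-rescue column is the comparator: scheduled readings and tied times already move 0.50 to about 0.53. In the most extreme cell, 29.8% of placebo and 53.1% of active challenges are actually rescued. With a true hazard ratio of 0.7 and a placebo median of 3 h, 0.713 becomes 0.727–0.797 when readings are counted and 0.699–0.713 when censored.

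**4. Sensitivity to when rescue is given.** In separate runs, true hazard ratio 0.5, with 10%, 25% or 40% of placebo challenges unrecovered at 3 h:

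- all rescued at 3 to 5 h, recovered 15 min later: 0.524, 0.589, 0.659 (censored at rescue: 0.493, 0.498, 0.501);
- half rescued at 3 to 5 h: 0.51, 0.54, 0.59;
- 10% to 25% rescued at 3 to 5 h: 0.49–0.54;
- 10% to 50% rescued at 7 to 8 h: 0.49–0.52 (censored: 0.49–0.51);
- all rescued at 7 to 8 h: 0.50–0.56.

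**5. AUC.** Take a fall D that decays exponentially to 5% at natural recovery time T, so k = ln(D/0.05)/T. If rescue at time r ends the area, the share kept is (1 − e^(−kr))/(1 − e^(−kT)).

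- D = 20%, T = 8 h, r = 3 h: k = ln(4)/8 = 0.173, share = 0.405/0.750 = 0.54.
- D = 30%, T = 4 h, r = 3 h: k = ln(6)/4 = 0.448, share = 0.739/0.833 = 0.89.

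Over falls of 20% to 30%, T of 4 to 8 h and r of 3 to 4 h, a rescued challenge keeps 54% to 89% of its area. For the geometric mean ratio, take the 1.5 h scenario with all assigned rescue: 29.4% of active and 9.7% of placebo challenges are rescued, an excess of 19.7 points. Ignoring covariates, the ratio is multiplied by exp(0.197 × ln 0.541) = 0.89 to exp(0.197 × ln 0.887) = 0.98.

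**The case against.** **Silence is not a rule.** A reader might infer that the plan treats bronchodilator recovery as natural recovery. No text says so. The censoring flag might cover rescue. The AUC calculation refers to a sponsor respiratory standard (001-MCG-163) that is not available, and SAP 7.8.5.2 points to a section 7.6.1 that is not in the public copy. SAP 6.2 also lets the blinded report planning and database lock meeting rule on discrepant values. This stands to the extent that only the visible text can be judged. It does not remove the point. An explicit 3 h limit implies that later readings stay in, and the time-to-recovery definition cites no standard. The meeting's remit is discrepant data and protocol deviations, and use of supplied rescue is neither.

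**The size may be nil.** A reader might also infer that slow recovery will be understated. That needs late rescue to occur and active drug to slow recovery, and the documents establish neither. Protocol 1.1 reports a rapid return to baseline in the animal model with and without drug. A subject at 93% of post-diluent is unrecovered for the endpoint, yet nothing requires rescue at that level. The discharge threshold, 90% of the day's first value, is a looser percentage, and discharge is scheduled only at 8 h. All of this stands: the larger shifts need slow recovery together with rescue of most subjects still unrecovered.

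**The consequence is limited.** The endpoints are secondary, Protocol 7.2 plans no confirmatory testing, and individual data are listed. This also stands.

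**Conclusion.** The gap is real. The visible plan has a 3 h rescue rule, 8 h of Day 2 readings, recovery definitions that ignore rescue, and an undefined censoring flag. Used as measured, late post-rescue readings would shorten recovery time and AUC0-tz. If active drug slows recovery, that pulls both comparisons towards no harm.

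With an assumed true hazard ratio of 0.5, the shift is essentially nil when few subjects are unrecovered at 3 h, and at most about 0.01 when up to half are rescued near 8 h. It reaches a move from 0.53 to 0.68 when the placebo median is 3 h and every subject unrecovered at 3 h is assigned rescue. These figures rest on exponential recovery and a prompt response to rescue, and the documents give no rate with which to choose among them.

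The documents do not support extending this to the primary endpoint. The maximum FEV1 reduction is very unlikely to occur after a late rescue, although that is a judgement, since no time-to-trough figure is given. This should be corrected in the SAP, but it affects exploratory secondary results only.

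**What to change.** In SAP 7.5:

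1. State that when rescue is given before recovery, at any time up to the last scheduled Day 2 reading, later FEV1 values cannot define recovery.
2. Define the flag: `cnsr` = 1 for such challenges. In the main analysis they are not recovered and are censored at 8 h; as sensitivity, censor at the time of rescue.
3. For AUC0-tz, flag these challenges and add a sensitivity analysis in which post-rescue readings cannot set tz. Carrying the last pre-rescue deficit forward is one option. It is a new convention, not the SAP's existing no-recovery rule, which imputes nothing, and it may overstate the area.
4. Report the number of such challenges by treatment.

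The cost is SAP wording and a little programming, because rescue clock times are already collected; no trial procedure changes. Neither censoring rule is free of assumptions. Censoring at rescue may be informative, since the slowest recoverers are the likeliest to be rescued. Holding them as unrecovered to 8 h may overstate slowness for those who would have recovered unaided. Showing both makes the dependence visible.
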